## **8 DATA HANDLING**

### **8.1 Source Documentation**

The Investigator must maintain source documentation of all study conduct and data and observations relevant to the study. This source documentation includes, but is not limited to, ICFs, original medical records, progress notes from the Investigator and study staff, laboratory reports, memory aids for solicited adverse events, and documentation of study vaccine accountability. The investigator may keep electronic source documentation per Sponsor's request.

### **8.2 Case Report Forms**

This study will employ electronic Case Report Forms (eCRFs) provided by the Sponsor. Certain clinical information requested in this protocol will be recorded on these eCRFs. The Investigator is responsible for the adequacy and accuracy of all data entered on the eCRFs. The Investigator is also responsible for signing all eCRFs, after which they will be locked to prevent further data entry or modification.

For further information on eCRFs, please refer to the PXVX-VC-200-006 CRF Completion Guidelines. For further information regarding data handling, please refer to the PXVX-VC-200-006 Data Management Plan (DMP).

### **8.3 Retention of Study Documentation**

The Investigator must make study data accessible to the monitor, other authorized representatives of PaxVax (and/or its designee), and regulatory agencies (e.g., FDA) inspectors upon request. A file for each subject must be maintained that includes the signed ICF and all source documentation related to that subject. The Investigator must ensure the reliability and availability of source documents from which the information on the eCRF was derived. Investigators are required to maintain all study documentation, including copies of eCRFs, ICFs, and adequate records for the receipt and disposition of all study medications, for a period of 2 years following the FDA or other regulatory approval of VAXCHORA, or 2 years after clinical development of VAXCHORA is discontinued, unless a longer period is required by applicable law or regulation. The Investigator will destroy study documentation only upon instruction by the Sponsor and must notify the Sponsor upon completion of such destruction. Subject identity information will be maintained for 15 years unless a longer period is required by applicable law or regulation.

### **8.4 Data Monitoring**

The Sponsor or designee will monitor completed eCRFs against source documentation at regular intervals throughout the study to verify adherence to the protocol, completeness, accuracy, and consistency of the data, and adherence to local regulations on the conduct of clinical research. The Investigator must make source documentation accessible to the Sponsor or designee as needed to verify the information in the eCRFs. The Investigator agrees to cooperate with the Sponsor or designee to ensure that any problems detected in the course of data monitoring are resolved.

### **8.5 Laboratory Data**

This study will employ electronic transfers of external laboratory data generated from clinical specimens collected by the Investigator. The Investigator is responsible for the adequacy and

accuracy of data associated with collection of these specimens. The Sponsor or designee is responsible for the adequacy and accuracy of the data generated by external laboratories.

### **8.6 Audit Compliance**

The Investigator must permit the Sponsor and/or designee, regulatory agencies, and/or the IRB direct access to facilities and study documentation for the purpose of auditing study conduct. Direct access includes examining, analyzing, verifying, and reproducing any records and reports that are needed for the evaluation of the study.

## 9 STATISTICAL ANALYSIS

### 9.1 Sample Size Calculation

Assuming that the true seroconversion rate among 12 to <18-year-olds is 92.4% or higher, the sample size of 143 evaluable vaccinees for that age cohort affords 93.3% power to demonstrate that the seroconversion rate within the group is non-inferior to the 94% rate observed in the 2687 adult subjects assessed in the PaxVax lot-consistency trial, PXVX-VC-200-004. The sample size allows for up to 5% of subjects to be not evaluable for the primary immunogenicity analyses in the two older cohorts (ages 6 to < 18). Based on the inevaluable rate observed to date, it is estimated that approximately 30% of subjects in the youngest cohort (ages 2 to < 6) will be inevaluable, mostly due to lack of consumption of the full dose. As defined in the alpha-spending strategy described in [Section 9.5.1](#), non-inferiority implies that the lower bound on the two-sided 96.7% confidence interval on the seroconversion rate among 12 to <18-year-olds is within 10 percentage points of the adult rate. Making similar assumptions about the true seroconversion rates in the other two pediatric age cohorts, and assuming that the rates in the three age cohorts are independent of one another, the overall power for demonstrating the non-inferiority of all three age cohorts is  $(93.3\%)^3 = 81\%$ .

To meet the other primary objective, the lower bound of the two-sided 98.3% confidence interval on the cohort-specific seroconversion rate must equal or exceed 70%. Under the same assumptions as above – in particular, assuming the true seroconversion rate within an age cohort is at least 92.4% – 143 evaluable vaccinees provide greater than 99.9% power to establish that the lower bound on the cohort-specific rate is at least 70%. Power is still greater than 99.9% when requiring the lower bound on all three cohorts to be 70% or greater.

The overall power of meeting both primary objectives in all three age cohorts can be approximated by multiplying the power of meeting the non-inferiority objective by the power of meeting the 70% lower bound objective:  $81\% \times 99.9\% \approx 81\%$ . Note that the calculations above rely on the assumption that seroconversion rate in one cohort is completely independent of the rate in another. Since that assumption is conservative, it is likely that the true power of the trial is higher than 81%.

Given a total of 510 subjects receive VAXCHORA, there is a 99% chance that an uncommon AE - one expected to occur in only 1% of vaccinees - will be observed at least once during the trial.

### 9.2 Treatment Period

The main study consists of a screening period of 30 days, Day 1 vaccination, an observation period from Day 1 to Day 29, and a follow-up period through Day 181. Placebo crossover has an optional active vaccination at Day 181 after unblinding, with a 6 month post vaccination follow-up period. Cohort 1 has an optional sub-study consisting of a long-term follow-up period through Day 730.

### 9.3 Treatment Groups

- Subjects in the active treatment group in each Cohort at Day 1 will receive VAXCHORA.

Cohort 1: 12 to <18 years (Active treatment group: n=150)

Cohort 2: 6 to <12 years (Active treatment group: n=150)

Cohort 3: 2 to < 6 years (Active treatment group: n=210)

- Subjects in the Placebo crossover group in each Cohort at Day 181 ( $\pm 7$ ) will be offered VAXCHORA.

Cohort 1: 12 to <18 years (Placebo crossover group: n=25)

Cohort 2: 6 to <12 years (Placebo crossover group: n=25)

Cohort 3: 2 to < 6 years (Placebo crossover group: n=35)

## 9.4 Safety Analysis

Safety will be assessed primarily through the evaluation of solicited and unsolicited AEs.

### 9.4.1 Solicited AEs

Solicited AEs recorded during Days 1-8 will be summarized. Specifically, a table will summarize the percent of subjects within each treatment group who experience each solicited adverse event at least once. A second table will present a similar summary constrained to solicited AEs of moderate severity or higher. An additional analysis will present the minimum, median and maximum number of days that subjects in each treatment group experience each type of solicited AE. The information regarding the incidence and severity of solicited AEs reported by Placebo crossover subjects between Days 181 and 188 will be summarized and listed.

### 9.4.2 Unsolicited AEs

Unsolicited AEs recorded through Day 29 will be summarized by treatment group, system organ class, preferred term and severity. Unsolicited AEs collected from Days 181 to 209 will be summarized separately for Placebo crossover subjects.

SAEs recorded through Day 181 or Day 365 (for Placebo crossover subjects) or Day 730 (for sub-study subjects) will be presented.

## 9.5 Immunogenicity Analysis

### 9.5.1 Primary Immunogenicity Analyses

Seroconversion will be defined as a 4-fold or greater rise in SVA over Day 1. Each rate will be accompanied by a 95% confidence interval (CI) calculated using the Wilson method (Agresti 1998).

1. The seroconversion rate between Day 1 and Day 11 for vaccinees in each of the 3 age cohorts will be compared to the seroconversion rate for vaccinees between the ages of 18 and 45 who participated in the lot consistency study PXVX-VC-200-004 by calculating the difference between the two rates and computing a 96.7% confidence interval for this difference.
2. For each of the 3 age cohorts, the proportion of vaccinated subjects who experience a 4-fold or greater increase in serum vibriocidal titer between Day 1 and Day 11 will be calculated, and a 98.3 % confidence interval on this proportion of seroconverters will be computed.

## Acceptance Criteria for Primary Analyses

1. The lower bound of the two-sided 96.7% confidence interval on the difference in seroconversion rates between children and adults must be greater than -10 percentage points.
2. The lower bound of the two-sided 98.3% confidence interval on the proportion of vaccinees who seroconvert between Day 1 and Day 11 must equal or exceed 70%.

### Alpha-Spending Strategy

In order to ensure that the total Type I error for the study is capped at  $\alpha = 0.05$ , 2/3 of the  $\alpha$  will be allotted to the primary objective of establishing non-inferiority relative to adults, and 1/3 of the  $\alpha$  will be allotted to the primary objective of demonstrating that the seroconversion rate equals or exceeds 70%. The two primary objectives will be evaluated independently, and within each primary objective, testing in the different age cohorts will proceed sequentially beginning with the data for the 12 to <18 age cohort, as follows:

1. Non-inferiority: the analysis of non-inferiority between vaccinees in the 12-18 age cohort and adults between the ages of 18 and 45 will be conducted first. Formal analysis of non-inferiority in the 6 to <12 age cohort will be performed only if the lower bound of the two-sided 96.7% confidence interval on the difference between the seroconversion rates for children in the 12 to <18 age cohort and adults equals or exceeds the pre-specified acceptance criterion. Formal evaluation of non-inferiority in the 2 to <6 age cohort will occur only if the acceptance criterion is met for both the 12 to <18 and 6 to <12 age cohorts. This strategy maintains the overall Type I error for the primary objective of non-inferiority at  $\alpha = 0.033$ .
2. Seroconversion Rate: the analysis of the seroconversion rate among vaccinees in the 12 to <18 age cohort will be conducted first. Formal analysis of the acceptability of the seroconversion rate in the 6 to <12 age cohort will be performed only if the lower bound of the two-sided 98.3% confidence interval on the seroconversion rate in the 12 to <18 age cohort meets the pre-specified acceptance criterion. Formal evaluation of the acceptability of the seroconversion rate in the 2 to <6 age cohort will occur only if the acceptance criterion is met for both the 12 to <18 and 6 to <12 age cohorts. This strategy maintains the overall Type I error for the primary objective concerning the magnitude of the seroconversion rate at  $\alpha = 0.017$ .

### 9.5.2 Secondary Analyses

For vaccinees in the age cohort 12 to <18, the point estimate of the seroconversion rate for vaccinees as well as the cumulative seroconversion rate will be computed at the time points Day 29, Day 91 and Day 181, and a 95% confidence interval will be constructed for each proportion. Pointwise seroconversion rates, cumulative seroconversion rates, and confidence intervals for placebo recipients in the age cohort 12 to <18 will be computed at Day 11, Day 29, Day 91 and Day 181. For vaccinees in the age cohorts 2 to <6 and 6 to <12, pointwise and cumulative seroconversion rates and corresponding confidence intervals will be calculated for Day 29. Pointwise seroconversion rates, cumulative seroconversion rates, and confidence intervals for placebo recipients in the age cohorts 2 to <6 and 6 to <12 will be computed at Day 11 and Day 29.

For vaccinees and placebo recipients in the age cohort 12 to <18, the GMT and 95% confidence interval will be computed for Day 1, Day 11, Day 29, Day 91 and Day 181, and the GMFI in each treatment group will be calculated for Day 11, Day 29, Day 91 and Day 181. For vaccinees and placebo recipients in the age cohorts 2 to <6 and 6 to <12, GMTs and 95% confidence intervals will be calculated for Day 1, Day 11 and Day 29, and GMFIs and corresponding confidence intervals will be calculated for Day 11 and Day 29. For participants in the sub-study, the GMT and 95% confidence interval and GMFI with 95% confidence interval will be calculated for Days 365, 547 and 730. Number of subjects with SVA titers less than the LLOQ will also be summarized for each collection timepoint.

### **9.5.3 Memory B Cell Concentration Analyses**

In the main study, anti-O1 LPS memory B cells will be assessed at Day 1 (prior to vaccination), at Day 91, Day 181 for a subset of subjects in Cohort 1 and at Days 365, 547, 730 for subjects in the active treatment group of Cohort 1 for the sub study. Point estimates of median percentage as well as median fold rise Day 1 to Day 91, Days 181, 365, 547, 730 will be presented.

### **9.6 Interim Analysis**

After the last subjects enrolled in Cohorts 1 and Cohort 2 have completed their Day 181 visit, a preliminary immunogenicity and safety analysis may be performed and report written to facilitate a regulatory submission. Due to the unblinding of subjects individually at Day 181, the subjects in Cohorts 1 and 2 will have already been unblinded prior to the analysis and the analysis will not affect the blind of the Cohort 3 subjects. The results of these analyses are not expected to alter the course of the trial.

## **10 ADDITIONAL INFORMATION**

### **10.1 Ethical Conduct of the Study**

The study will be performed in accordance with the protocol and consistent with ICH Good Clinical Practice (GCP) Guidelines and applicable local regulatory requirements and laws.

### **10.2 IRB Oversight**

The study (protocol, informed consent form, recruiting materials, and any documents seen by the subject) will be reviewed and approved by an IRB appropriate to each study site. Subjects will not be recruited, consented, screened, or enrolled until the IRB has approved the required documentation. In addition, the IRB will review amendments to the protocol before their implementation.

The Investigator will retain all correspondence with the IRB in the regulatory binder and forward copies of all IRB approvals to the Sponsor.

### **10.3 Informed Consent and Assent**

The Sponsor will provide a master parent/guardian Informed Consent Form (ICF) template to each site for development of a site-specific parent/guardian ICF. The Sponsor will also provide informed assent form (IAF) templates to each site for development of site-specific and age-appropriate assent forms.

All site-specific ICFs and IAFs must be approved by the Sponsor and the IRB and must be in compliance with ICH GCP, local regulatory requirements and legal requirements. The Sponsor will advise the Site of required changes to the master ICF and IAF templates during the course of the study.

The Investigator will ensure that each potential study participant is fully informed about the nature and objectives of the study and possible risks associated with participation. Before informed consent is obtained, the Investigator, or a qualified person designated by the investigator, will provide the potential study participant with ample time and opportunity to inquire about the details of the trial, and will answer all relevant questions to the potential study participant's satisfaction. The potential study participant will then decide whether or not to participate in the trial. The Investigator, or a qualified person designated by the Investigator, will obtain written informed consent from each study participant before any study-specific activity is performed.

The Investigator will retain the original and any amended signed and dated ICFs and IAFs at the study site and provide a copy to each study participant.

### **10.4 Subject Confidentiality**

The Investigator will ensure that each subject's anonymity is maintained. On eCRFs and other documents submitted to the Sponsor and/or its designee, subjects must be identified by subject number only. For documents that are not for submission to the Sponsor and/or its designee (e.g., signed ICFs), the Investigator must maintain these documents securely and in compliance with Federal regulations and ICH GCP Guidelines.

### **10.5 Compensation for Injury**

The Sponsor will adhere to local regulations and guidelines regarding clinical trial compensation to subjects whose health is adversely affected by taking part in the study. The applicable policy for compensation for injury will be described in the master ICF template.

### **10.6 Clinicaltrials.gov**

For purposes of reporting to clinicaltrials.gov, the Sponsor is the responsible party and will provide information regarding this study in accordance with applicable regulations.

### **10.7 Public Disclosure and Publication Policy**

All publication rights are delineated in the Clinical Study Agreement. Sponsor or its designee shall have the right to publish or otherwise publicly disclose the information contained in or related to the Study Vaccine, the Study Data, or other Confidential Information in any form without the written consent of Site, the Principal Investigator or any other person. Each of the Sites and the Principal Investigator further agrees that Sponsor shall have the exclusive right to commercialize any products or services that are based upon, or derived from the Study Vaccine, the Study Data, or other Confidential Information.

### **10.8 Amendments**

The protocol may be amended only by the Sponsor. Agreement from the Investigator must be obtained for all protocol amendments and amendments to the Informed Consent document. The IRB must generally be informed of all amendments prior to implementation. In addition, the Investigator must obtain IRB approval for any amendments likely to affect the safety of study participants prior to implementation.

The Investigator or Sponsor may implement an amendment prior to IRB notification or approval only in order to eliminate an apparent immediate hazard to study participants. In that event, the Investigator must notify the IRB and Sponsor in writing within 7 calendar days after the implementation. Amendments, including descriptions and rationales, will be documented in this section of the protocol. The Investigator must send a copy of the approval letter from the IRB to PaxVax (or its designee).

### **10.9 Annual Progress Report**

PaxVax will submit a summary of the progress of the trial to the IND on file with the FDA once a year. In addition, the Investigator is responsible for submitting progress reports at least annually to the IRB and IBC that approved the study. Information will be provided on the date of inclusion of the first subject, numbers of subjects included and numbers of subjects that have completed the trial, SAEs and serious adverse reactions, other problems, and amendments.

### **10.10 End of Study Report**

The Investigator will notify their IRB and IBC of the end of the study and will submit a final report using the forms and/or format specified. The end of the study is defined as the last subject's last visit. In case the study is ended prematurely, the Investigator will notify the IRB and IBC, including the reasons for the premature termination.

Vital Signs		X 	X						X PC				
Con Med Evaluation		X 	X 	X	X	X c	X	X	X PC	X PC	X PC	X PC	X PC
Urine pregnancy test d		X 	X						X PC				
Vaccination			X						X PC				
Acceptability/Palatability			X						X PC				
Memory Aid a			X	X				X b	X PC	X PC			
Solicited AEs			X					X b	X PC				
Adverse Event Evaluation			X	X	X	X c	X	X	X PC	X PC	X PC	X PC	X PC
SVA			X	X	X			X					

X = All Subjects; PC = Placebo crossovers only; D/C = discontinuation; SVA = serum vibriocidal antibodies

 May be conducted at Day 1

 Updated as needed

PC placebo crossover subjects are offered VAXCHORA

a All subjects: issued at Day 1, reviewed at Day 11

b Only if between Day 1 and Day 11 (All subjects)

c Telephone contact required; in-person visit as clinically indicated

d for females of child-bearing potential

181PC: Placebo crossover Vaccination (Day 1)

191PC: Placebo crossover 10 days after Vaccination

209PC: Placebo crossover 28 days after Vaccination

271PC: Placebo crossover 90 days after Vaccination

365PC: Placebo crossover 180 days after Vaccination

COHORT 3 2 to <6 years	Study Day:	Screening	1	11	29	91 Phone FU	181	Early D/C	181 PC	191 PC	209 PC	271 PC Phone FU	365 PC Phone FU
Window (days):		-30	0	0	±2	±7	±7	n/a	±7	0	±2	±7	±7
Informed Consent/Assent		X 											
Medical History		X 	X 										
Inclusion/Exclusion		X 	X										
Physical Exam		X 	X 										
Vital Signs		X 	X						X PC				
Con Med Evaluation		X 	X 	X	X	X c	X	X	X PC	X PC	X PC	X PC	X PC
Vaccination			X						X PC				
Acceptability/Palatability			X						X PC				
Memory Aid a			X	X				X b	X PC	X PC			
Solicited AEs			X					X b	X PC				
Adverse Event Evaluation			X	X	X	X c	X	X	X PC	X PC	X PC	X PC	X PC
SVA			X	X	X			X					

X = All Subjects; PC = Placebo crossovers only; D/C = discontinuation; SVA = serum vibriocidal antibodies

 May be conducted at Day 1

 Updated as needed

PC placebo crossover subjects are offered VAXCHORA

a All subjects: issued at Day 1, reviewed at Day 11

b Only if between Day 1 and Day 11 (All subjects)

c Telephone contact required; in-person visit as clinically indicated

d for females of child-bearing potential

181PC: Placebo crossover Vaccination (Day 1)

191PC: Placebo crossover 10 days after Vaccination

209PC: Placebo crossover 28 days after Vaccination

271PC: Placebo crossover 90 days after Vaccination

365PC: Placebo crossover 180 days after Vaccination

**APPENDIX B: TOXICITY GRADING SCALE****Table for Clinical Abnormalities**

VACCINE REACTION	MILD (Grade 1)	MODERATE (Grade 2)	SEVERE (Grade 3)	POTENTIALLY LIFE THREATENING (Grade 4)
Abdominal Pain	Mild, no interference with activity	Some interference with activity	Significant, prevents daily activity	ER visit or hospitalization for hypotensive shock
Anorexia (Lack of appetite)	No interference with activity	Some interference with activity	Significant, prevents daily activity	ER visit or hospitalization
Diarrhea	4 loose stools /24 hours	5 loose stools/24 hours	≥ 6 loose stools/24 hours	ER visit or hospitalization
Fatigue (Tiredness)	Mild, no interference with activity	Some interference with activity	Significant, prevents daily activity	ER visit or hospitalization
Fever	> 100.4 – 101.1°F (≥ 38.0 –38.4°C)	≥101.2 – 102°F (≥ 38.5 –38.9°C)	≥ 102.1°F–104°F (≥ 39°C–40°C)	> 104°F (> 40°C)
Headache	Mild, no interference with activity	Some interference with activity	Significant, prevents daily activity	ER visit or hospitalization
Myalgia	Mild, no interference with activity	Some interference with activity	Significant, prevents daily activity	ER visit or hospitalization
Nausea	Mild, no interference with activity	Some interference with activity	Significant, prevents daily activity	ER visit or hospitalization for hypotensive shock
Vomiting	1–2 episodes/24 hours	> 2 episodes/24 hours	Requires IV hydration	ER visit or hospitalization for hypotensive shock "

When developing this Toxicity Grading Scale, PaxVax referred to the recommendations in the FDA’s Guidance for Industry: Toxicity Grading Scale for Healthy Adult and Adolescent Subjects Enrolled in Preventive Vaccine Clinical Trials ([US FDA 2007](#)).

Diarrhea 1-3 Stools/24 hours: Record as “loose stools” on the AE CRF.

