### 5.13 Solicited Adverse Events

Solicited adverse events for this study are: abdominal pain, nausea, vomiting, diarrhea, headache, lack of appetite, tiredness, and fever. From Day 1 through Day 8 (for all subjects) and from Day 181 through Day 188 (for Placebo crossover subjects), these adverse events will be solicited from subjects daily in the evening. Before discharge from the clinic on Day 1, all subjects will be trained to complete a memory aid to observe, measure, and record solicited AEs from Day 1 through Day 8. Study staff will review the signs and symptoms recorded on the memory aid with the subject to confirm severity and relationship to study vaccine, and action taken for the AE. The memory aid will be collected as a source document. Solicited adverse events from Day 1 through Day 8 will be recorded on the solicited adverse event eCRF. Symptoms continuing beyond Day 8 will be recorded on the adverse event eCRF. Actions taken for solicited AEs after Day 8 should be noted in the eCRF. Memory aid re-distribution and retraining to collect solicited adverse events from Day 181 through Day 188 (7 days after vaccination) will be done at Day 181 (vaccination) for Placebo crossover subjects. It will be reviewed by the study staff at the Day 191 (10 days after vaccination) visit.

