## 7.2 Severity Grading

The Investigator will grade all adverse events for severity. Adverse events listed in the Toxicity Grading Scale in [Appendix B](#) will be graded according to the criteria in the table. Adverse events not listed in the Toxicity Grading Scale will be graded as follows:

- Mild (Grade 1) – No interference with activity
- Moderate (Grade 2) – Some interference with activity
- Severe (Grade 3) – Significant; prevents daily activity
- Potentially Life-Threatening (Grade 4) – ER visit or hospitalization
- Fatal (Grade 5)

These severity grades also apply to the Study Stopping Rules in [Section 7.10](#).

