## 7.10 Study Stopping Rules

Enrollment will be stopped for any of the following:

1. Any death or SAE experienced by a subject, regardless of causality;
2. One or more subjects with a Grade 3 (severe) or greater AE assessed as possibly or probably related to the study vaccine.

The investigator or designee must suspend enrollment and notify the Medical Monitor at [REDACTED] within 24 hours of becoming aware of an event that meets either of the above rules. No specific notification form is required. Enrollment may be resumed following review of available safety data by the Sponsor's Medical Monitor and Safety Monitoring Committee and after the Sponsor's Medical Monitor has notified the Investigator that enrollment may resume.

For further information regarding Safety procedures, please refer to the PXVX-VC-200-006 Safety Management Plan (SMP) and PXVX-VC-200-006 SMC Charter.

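### Appendix B's entry threshold for fever contradicts itself at 100.4°F / 38.0°C, and two higher grade limits differ between units by conversion rounding

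*Protocol*

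**What the plan says.** The fever row of Appendix B gives each grade in both units:

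- Grade 1: "> 100.4 – 101.1°F (≥ 38.0 –38.4°C")
- Grade 2: "≥101.2 – 102°F (≥ 38.5 –38.9°C")
- Grade 3: "≥ 102.1°F–104°F (≥ 39°C–40°C")
- Grade 4: above 104°F, with above 40°C in brackets

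Section 7.2 makes this table binding: "Adverse events listed in the Toxicity Grading Scale in [Appendix B](#) will be graded according to the criteria in the table". It also carries the same grades over to the stopping rules.

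Fever is one of the eight events in Section 5.13: "Solicited adverse events for this study are: abdominal pain, nausea, vomiting, diarrhea, headache, lack of appetite, tiredness, and fever". Section 9.4.1 counts subjects with each solicited event at least once and then adds: "A second table will present a similar summary constrained to solicited AEs of moderate severity or higher". Section 7.10 stops enrollment for, among other things: "One or more subjects with a Grade 3 (severe) or greater AE assessed as possibly or probably related to the study vaccine".

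Section 5.8 specifies oral or axillary measurement by age but no unit. Section 5.13 has families record solicited events on a memory aid and again states no unit. No section names a governing unit or a rounding rule.

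**The concern.** A scale printed in two units works only if both columns give the same grade for the same temperature. Here the lowest limit is strict in Fahrenheit and inclusive in Celsius at the same physical temperature. That limit decides whether a child enters the fever incidence table at all.

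The next two limits also fail to convert exactly. The Grade 1/2 limit decides entry into the moderate-or-higher table. The Grade 2/3 limit decides whether a fever judged related meets the rule in Section 7.10. One event is enough to trigger that rule, so a borderline reading is not averaged over a count of events.

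**Working it through.** **Inputs.** The four paired limits are those in the fever row of Appendix B. The conversions are C = (F − 32) × 5/9 and F = C × 9/5 + 32.

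**Where the plan's own figures reproduce.** The upper ends of Grades 1 and 2 convert as printed, to one decimal:

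- 101.1°F: 69.1 × 5/9 = 38.39, printed as 38.4°C
- 102°F: 70 × 5/9 = 38.89, printed as 38.9°C

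The Grade 3/4 limit agrees exactly: 104°F is 72 × 5/9 = 40.0°C, with a strict sign in both units.

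**Entry threshold (no fever / Grade 1).** 100.4°F is 68.4 × 5/9 = 38.0°C exactly. The Fahrenheit rule requires more than 100.4, so the reading is not fever. The Celsius rule requires 38.0 or more, so it is Grade 1. No rounding is involved, and the conflict appears whichever unit the thermometer shows.

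**Grade 1/2 limit.** 101.2°F is 69.2 × 5/9 = 38.44°C. It is Grade 2 in Fahrenheit. In Celsius it is below the 38.5 limit, and rounded to 38.4 it is Grade 1. In reverse, 38.5 × 9/5 + 32 = 101.3°F.

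**Grade 2/3 limit.** 102.1°F is 70.1 × 5/9 = 38.94°C. It is Grade 3 in Fahrenheit. In Celsius it is below the 39 limit, and rounded to 38.9 it is Grade 2. In reverse, 39 × 9/5 + 32 = 102.2°F.

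**Full scan.** Every 0.1°F reading from 99.0 to 105.9 and every 0.1°C reading from 37.0 to 41.1 was graded in both columns, with the converted value both unrounded and rounded to one decimal.

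| Reading | Converted value | Grade by Fahrenheit column | Grade by Celsius column |
|---|---|---|---|
| 100.4°F | 38.0°C | none | 1 |
| 101.2°F | 38.44°C | 2 | 1 |
| 102.1°F | 38.94°C | 3 | 2 |
| 38.0°C | 100.4°F | none | 1 |

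No other reading disagrees. Among Celsius readings to one decimal, only 38.0°C is discordant. So the upper two mismatches arise only for a reading taken in Fahrenheit and then graded in Celsius. Before rounding, 38.44 and 38.94 fall in the gaps between the printed Celsius ranges (38.4 to 38.5, and 38.9 to 39).

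**The case against.** The strongest reply is that little of this need ever show up in the data. All sites are in the US and the table lists Fahrenheit first. If every reading is taken and graded in one unit, each 0.1-degree reading has one grade and no child is classified two ways. The recording unit may be set in the CRF completion guidelines or the data management plan, which Section 8.2 cites and which are not shown. Fever is summarized descriptively and enters no primary acceptance criterion. Staff who assess events are blinded, so a one-reading ambiguity should not systematically favor either arm.

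Most of that stands, and it limits the size of the point. It does not remove the conflict at the entry threshold, because the protocol makes the table binding and does not say which column prevails.

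Three stronger readings are tempting, and the documents do not support them:

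- **Three equal contradictions.** A reader might count three of the four limits as contradictory in the same sense. Only the lowest is a true conflict. The other two need a conversion step that the protocol never prescribes.
- **Sites using different units.** A reader might infer that sites record in different units. Nothing in the protocol shows this.
- **Study-wide suspension.** A reader might infer that one reading of 102.1°F would halt enrollment at every site. Section 7.10 says that enrollment stops and that the investigator must suspend it and notify the medical monitor. It does not spell out a study-wide halt, and enrollment may resume after review.

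**Conclusion.** The point holds in limited form. The entry threshold for solicited fever contradicts itself at exactly one temperature, 100.4°F or 38.0°C, and this follows from the printed text without any assumption. The Grade 1/2 and Grade 2/3 limits differ by conversion rounding, and only the readings 101.2°F and 102.1°F are affected. Those two matter only on the assumption that Fahrenheit readings are converted before grading. On that assumption, 102.1°F could be Grade 3 or Grade 2 for Section 7.10, with a consequence only if the fever is also judged possibly or probably related while enrollment is open.

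How many children would have such readings cannot be estimated from the protocol. The point deserves correction because the row defines a safety endpoint and feeds a single-event rule. It has no bearing on the primary immunogenicity analyses.

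**What to change.** Reconcile the inequality signs at 100.4°F / 38.0°C so that both columns treat that temperature alike. Name one unit as governing for grading and have every reading graded in that unit, for example by a derivation in the EDC system, with the other column shown only as its conversion. Then check the row against Sections 7.2, 7.10 and 9.4.1. Which cut-point applies is the sponsor's decision.

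The cost is one table row and one derivation. The change is not wholly neutral: the choice may alter how a borderline reading is graded, including under Section 7.10, so it should be recorded as a change to the grading scale. If readings have already been graded, they should be regraded from the recorded temperature and unit.
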